3. STUDY DESIGN

3.1. Study Design and Population

ADU-CL-14 is an open-label, single-arm, multicenter clinical study in approximately 79 adults with recurrent or metastatic gastric, gastroesophageal junction (GEJ), or esophageal adenocarcinomas who have received one or two prior systemic chemotherapy treatment regimens for advanced disease. Of the approximately 79 evaluable subjects, the study will seek to enroll approximately 50 subjects with gastric/GEJ adenocarcinomas and approximately 29 subjects with esophageal adenocarcinoma to achieve adequate representation of each tumor type.

The study design consists of a 28-day Screening Period, Treatment and Evaluation Period (including a Safety Run-in), and a Follow-up Period. CRS-207 and pembrolizumab will be administered in 3-week cycles. For Cycle 1, pembrolizumab (200 mg) will be administered by IV over 30 minutes on Day 1 and CRS-207 (starting dose 1×10^9 CFU) will be administered IV over 1 hour on Day 2. If the infusions are well tolerated, pembrolizumab and CRS-207 may be administered on the same day (Day 1) for subsequent cycles. After 4 cycles, pembrolizumab will continue to be administered on Day 1 at each treatment cycle (every 3 weeks; Q3W), and CRS-207 will be administered once every 6 weeks (i.e. every other treatment cycle; Q6W).

Treatment cycles will continue for up to 24 months as long as there is adequate safety and potential for clinical benefit. If radiographic disease progression is observed, clinically stable subjects who meet dosing eligibility may continue to receive CRS-207 and pembrolizumab according irRECIST guidelines. Subjects who experience an unacceptable toxicity directly attributable to either pembrolizumab or CRS-207 may continue on study and receive either pembrolizumab or CRS-207 as single agent study treatment with approval by the Medical

Sponsor: Aduro Biotech, Inc.
Protocol Number: ADU-CL-14
Version and Date: Version 1.0, 13Mar2018

Monitor. Alternatively, study drug administration may revert back to consecutive day-dosing regimen as performed in Cycle 1 (Day 1 pembrolizumab and Day 2 CRS-207).

The Treatment and Evaluation Period is defined as the time from Day 1 until discontinuation of both CRS-207 and pembrolizumab, completion of an End-of-Treatment (EOT) Visit, and documented disease progression.

Blood will be collected at EOT to assess clearance of CRS-207 [REDACTED]

[REDACTED]. The EOT Visit will occur no more than 28 days after the last dose of study drug. If the subject has discontinued CRS-207 but continues on pembrolizumab, the subject will be asked to come back to the clinic for CRS-207 blood cultures 7 days after the last CRS-207 dose [REDACTED]

[REDACTED]. If the subject begins another anticancer therapy before the end of the 28-day period, all EOT Visit assessments should be completed prior to commencing the new therapy. Unresolved AEs will be monitored until resolution or confirmed stability of the event. Subjects that discontinue all study drugs and complete the EOT without documented progressive disease (based on RECIST v1.1) will be asked to complete Evaluation Visits for tumor imaging every 6 weeks until documented disease progression or start of another anticancer therapy. To eliminate any potentially residual CRS-207, subjects will be administered a 7-day course of antibiotics beginning at the EOT visit or 7 days after the last dose of CRS-207 (for patients continuing on pembrolizumab) and prior to receiving any subsequent cancer-related therapy.

At the end of the Treatment and Evaluation Period subjects will enter the Follow-up Period of the study and will be followed for survival, subsequent cancer-related therapies, and post treatment monitoring for CRS-207 [REDACTED] until death or close of study by the Sponsor. The Sponsor may request survival status be assessed at additional time points during the course of the study. Sites will attempt to obtain vital status data from public records or other external sources where possible if a subject withdraws consent from study (i.e. refuse follow-up for vital status) or is documented as lost to follow up. Follow-up will continue for at least 12 months from last dose of study drug.

A Safety Run-in will be completed since there are no precedent data on the use of pembrolizumab with CRS-207. Subjects will be monitored for unacceptable toxicity during the first 28 days (through 7 days after the Cycle 2 dose). During the Safety Run-in, evaluable subjects are defined as those who remain on study for the 28-day monitoring period, subjects with unacceptable toxicity, and subjects who are discontinued for safety reasons at the Investigator's discretion (even if criteria for unacceptable criteria are not met). Treatment of the first 6 subjects that are followed for the 28-day period will be staggered with no more than 1 subject treated per week. In the event that 4 in up to 12 safety-evaluable subjects experience an unacceptable toxicity, the subsequent cohort of 12 subjects enrolled will be administered CRS-207 at a dose reduced by a half-log. In the event of 4 subjects in up to the next 12 safety-evaluable subjects enrolled experience an unacceptable toxicity, the subsequent cohort of 12 subjects enrolled will be administered a reduced dose of CRS-207. For each dose reduction (to a minimum of 1×10^8 CFU) the first 12 subjects will be treated and unacceptable toxicities assessed as described above. No adjustments will be made to the pembrolizumab dose.

Sponsor: Aduro Biotech, Inc.
Protocol Number: ADU-CL-14
Version and Date: Version 1.0, 13Mar2018

Safety data and all unacceptable toxicities will be reviewed by a Safety Review Team (SRT) comprised of participating investigators in the study, the Medical Monitor, and Sponsor representatives. Once the Safety Run-in is complete, safety will continue to be evaluated on an ongoing basis in this open-label study. Cumulative clinical experience with CRS-207 and pembrolizumab will be used to assess whether AEs are considered expected.

The schedule of events is provided in the protocol. Subjects who experience tolerability issues with same-day dosing may continue to follow the consecutive-day dosing regimen as in Cycle 1 with Day 1 pembrolizumab followed by Day 2 CRS-207 dosing.

Tumor imaging and evaluation will be assessed at Screening and during the Treatment and Evaluation Period approximately every 6 weeks after initiation of study drug. Tumor measurement and assignment of response will be determined by local Investigators. For subjects on treatment more than 12 months, the frequency of imaging may be reduced to every 12 weeks. Peripheral blood will be collected to assess immune responses directed against *Listeria monocytogenes*, mesothelin, and other tumor-associated antigens. Archived tumor tissue and paired tumor biopsies (collected at Screening and during Cycle 2) will be used to explore the association of PD-L1 expression, mesothelin expression, and TIL characteristics with clinical responses.

3.2. Randomization and Blinding

ADU-CL-14 is a single-arm, open-label study. Since all subjects will receive the same investigational products, randomization and blinding are unnecessary; study drug will be provided open-label.

3.3. Sample Size Considerations

This study is descriptive in nature, as such the sample size for this study is determined by practical rather than statistical considerations. Approximately 79 subjects will be enrolled to achieve at least 79 treated subjects with evaluable post-baseline tumor data. With 79 subjects, the precision for point estimate for ORR is as follows: the 95% confidence interval (CI) width for ORR based on Wilson score intervals are at most the observed proportion +/- 0.108. If the observed ORR = 30.4% (24 of 79 subjects with PR or CR), the lower bound of the 95% CI would be 19.5%.

Of the 79 subjects enrolled, an estimated 50 subjects will be enrolled with gastric or GEJ cancer, and an estimated 29 subjects will be enrolled with esophageal cancer. Assuming at least 50 evaluable gastric/GEJ subjects are evaluable for ORR, the precision for point estimate for ORR is as follows: the 95% CI width for ORR based on Wilson score intervals are at most the observed proportion +/- 0.134. Assuming at least 29 evaluable esophageal cancer subjects are evaluable for ORR, the precision for point estimate for ORR is as follows: the 95% CI width for ORR based on Wilson score intervals are at most the observed proportion +/- 0.173.

Sponsor: Aduro Biotech, Inc.
Protocol Number: ADU-CL-14
Version and Date: Version 1.0, 13Mar2018

3.4. Interim Analysis

A Safety Review Team will monitor data during the study, as described in Section 3.1. Otherwise, no other formal interim analysis activities are planned per the protocol.

3.5. Timing of Analyses

On 12 December 2017, Aduro decided to cease development activities of CRS-207 and close out ongoing studies. As of 31 January 2018 every subject had completed their end of treatment visit. No additional follow-up of these subjects is expected. This ASAP details the analysis plans for the CSR synopsis as of the final database lock.

4. DATA ANALYSIS CONSIDERATIONS

All analyses will be conducted based on SAS 9.3 or higher.

All data in the database will be presented in by-subject data listings.

Unless otherwise stated, all listings will be sorted by site ID, subject number, and assessment date (and time, if available).

Unless stated otherwise, continuous data will be summarized based on n, mean, median, standard deviation (SD), first quartile (Q1), third quartile (Q3), minimum value, and maximum value. For continuous variables, if n=1, the SD cannot be calculated and will be displayed as (NA).

Unless stated otherwise, categorical data will be summarized using n and percentage based on the number of nonmissing values.

- The number of missing values will be presented as a separate category with no percentage, but only if one or more subjects are missing data.
- Counts of zero will be presented without percentages.

Precision

- Mean, Median, Q1, and Q3: one additional decimal place to that reported for Minimum and Maximum
- SD: two additional decimal places than the Minimum and Maximum
- Percentages: reported to one decimal place

No statistical significance test will be performed.

With exception to missing data handling noted in section 5.6, data will not be imputed for analysis purposes.

Summaries by visit will be produced for sample sizes ≥ 2 .

Sponsor: Aduro Biotech, Inc.
Protocol Number: ADU-CL-14
Version and Date: Version 1.0, 13Mar2018

Numbering for data displays will be based on ICH E3.

4.1. Stratification and Covariates

There are no formal plans for analysis stratification.

4.2. Evaluation of Subgroups

Subgroup analyses are not planned to be performed for the final analysis.

4.3. Multiple Comparisons and Multiplicity

Not Applicable.

5. GENERAL DATA HANDLING CONVENTIONS

5.1. Assigned and Actual Treatment

All subjects enrolled in the study are assigned to combination therapy.

5.2. Reference Dates

- Age and time from diagnosis of disease will use the enrollment date as their reference date.
- Safety data, such as AEs and laboratory assessments will use the first date of study treatment as a reference date.
- Efficacy data will use the first date of study treatment as a reference date.
- Study Day will use the first date of study treatment.

5.3. Study Day and Duration Variables

Reference date calculations will be defined as the following:

- date of interest – reference date + 1 when the date of interest \geq reference date;
- otherwise, date of interest – reference date.

For instance, study day will be based on the date of first study treatment as the reference would either have a negative value if collected before dosing or a positive value if collected after drug dosing; there will be no study day zero.

Duration of time is dependent on reference dates and will be calculated in a manner similar to that of the reference date calculation, assuming that dates of interest will strictly follow reference dates (e.g. no negative values). For example, duration on study is defined as the end of study date – enrollment date + 1. Duration of treatment is defined as the last date of treatment – first dose date + 1. Duration of the safety observation period is defined as (the last date of treatment

Sponsor: Aduro Biotech, Inc.
Protocol Number: ADU-CL-14
Version and Date: Version 1.0, 13Mar2018

+ 28 days) – first dose date + 1. Subjects still receiving ongoing treatment or participating in study follow up at the time of analysis will use imputed treatment end and end of study dates as described in section 5.6.

Survival, or time-to-event, endpoints such as PFS or OS are followed until first event or censoring. As a result, survival time will be calculated as: event or censoring date – reference date + 1. These are further described in Section 7.

When reporting survival or duration outcomes, the results (in days) above will be converted to an appropriate unit. When reporting in months it will be divided by 30.4375; for reporting in weeks it will be divided by 7; and for reporting in years it will be divided by 365.25.

5.4. Study Time Periods

Safety reporting will be classified by the following study periods for analysis:

Pre-therapy is defined as the period prior to a subject's first dose of study treatment.

On-therapy is defined as the period between first dose of study treatment and within 28 days following the last dose of study treatment.

Post-therapy is defined as the period of time following the on-therapy period.

5.5. Baseline, Post-Baseline Changes, and Endpoint

Baseline will be based on the last nonmissing value collected prior to or on the date [and time, if applicable] of first study treatment. Post-baseline values will be those collected after first dose of study drug.

Change from baseline is defined as: value – baseline value.

Percentage change from baseline is defined as: (value – baseline value)/baseline value X 100%.

Most extreme change: The maximum most extreme change will be the maximum post-baseline value; the minimum most extreme change will be the smallest post-baseline value. This calculation will consider all assessments collected within the on-therapy period, scheduled or unscheduled.

5.6. Imputation of Partial Dates

Adverse Events and Concomitant Medications

- If the AE start date is completely missing, no imputation will be conducted.
- If the AE start date is missing day and month, do the following:
 - If the treatment start date is missing or the AE year does not fall in the same as that of first treatment or if the AE contains information to indicate that the event

Sponsor: Aduro Biotech, Inc.

Protocol Number: ADU-CL-14

Version and Date: Version 1.0, 13Mar2018

ended before the date of first study treatment (e.g. AE end date month and year are earlier than the treatment start date or the full date is known and occurs earlier than the date of first treatment), then set the start month and day to January 1st

- Otherwise, set the start date to the date of first study treatment
- If only the day is missing, do the following:
 - If the study treatment start date is missing or the month and year does not fall in the same as that of first treatment or if the AE contains information to indicate that the event ended before the date of first study treatment, then set the start month and day to the 1st of the stated month
 - Otherwise, set the start date to the date of first study treatment
- End dates will not be imputed

Subsequent Anticancer Therapy, Radiotherapy or Anticancer Surgical Procedures

Partial dates for subsequent therapies will not typically be imputed, but may be needed to support efficacy outcome derivation for oncology studies. This typically applies to anti-cancer therapy and radiotherapy, but may also apply to surgical procedures. In this case, the following will be applied for imputation of new anti-cancer therapies taken after first study treatment:

- If the start date is completely missing, no imputation will be conducted
- If the start date is missing day and month, do the following:
 - If progressive disease (PD) has been identified in the year noted, new anti-cancer therapy date will be assigned to begin one day after the date of PD.
 - Otherwise the new anti-cancer therapy date will be assigned to January 1st.
- If only the day is missing, do the following:
 - If PD has been identified in the year noted, new anti-cancer therapy date will be assigned to begin one day after the date of PD.
 - Otherwise the new anti-cancer therapy date will be assigned to the 1st of the stated month.

Overall Response Date

For each visit-specific disease assessment, the date of overall response will need to be established. For CR and PR, set the date of overall response to the latest of all tumor assessments for the specified visit. Otherwise, set to the earliest date of all assessments made during the specified visit.

Treatment End Date

Missing treatment end dates will not be imputed at the end of the study. However, due to ongoing reporting needs, treatment end date will be imputed as the earliest of the data cutoff date, date of death, or date of study treatment withdrawal.

Sponsor: Aduro Biotech, Inc.
Protocol Number: ADU-CL-14
Version and Date: Version 1.0, 13Mar2018

End of Study Date

Missing study end dates will not be imputed at the end of the study. However, due to ongoing reporting needs, end of study dates will be imputed as the earliest of the data cutoff date or date of death.

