7.1. Primary Efficacy Endpoint

The primary efficacy endpoint and efficacy endpoints will be derived and listed but not summarized.

Objective Response Rate

A subject's BOR is determined by the highest qualitative value assessed during the study given a hierarchy of overall response results: CR > PR > SD > PD > NE. Response will be defined according to RECIST v1.1. In order for a valid value of SD to be assigned, there must be evidence of stable disease for at least 6 weeks. If the minimum time for SD has not been met on the first assessment, the assignment of BOR will depend on subsequent response assessments.

Sponsor: Aduro Biotech, Inc.
Protocol Number: ADU-CL-14
Version and Date: Version 1.0, 13Mar2018

Subjects which do not have follow up data after a first assessment of SD prior to the minimum time requirement will be considered as not evaluable. BOR will be based on assessments collected after the first dose of study until disease progression; assessments collected after the start of new cancer treatment will not be considered.

Objective response is achieved for subjects who have a BOR of CR or PR according to RECIST v1.1. ORR is defined as the number of subjects who exhibit a BOR response of CR or PR divided by the number of subjects evaluable for analysis and will not be summarized or reported in the CSR synopsis.

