7.2. Secondary Efficacy Endpoints

Disease Control Rate

Disease control is achieved by subjects who exhibit a BOR of CR, PR, or SD according to RECIST v1.1. DCR is defined as the number of subjects who exhibit a BOR response of CR, PR, or SD divided by the number of subjects evaluable for analysis and will not be summarized or reported in the CSR synopsis.

Progression Free Survival

PFS is defined as the number of weeks from the date of first dose of study treatment to the first date of objectively determined progressive disease according to RECIST v1.1 or death from any cause and is computed as described in Section 5.3. The primary analysis of PFS will include tumor assessments collected after the end of study treatment. Tumor assessments taken after switch to another anti-cancer therapy will be excluded from consideration.

The first date of objectively determined progressive disease would be the earliest date of any post-baseline overall response finding of progressive disease as part of the tumor lesion assessment data or death, unless a subject is censored at an earlier date. If an assessment occurs over several days, the method described in Section 5.6 will be used. If there are no adequate assessments for a subject, they will be censored on their first dose date unless they died prior to having their first assessment (in which case they will be considered to have had a PFS event of death). If a subject receives subsequent anticancer therapy prior to documentation of progressive disease, PFS will be censored at the latest adequate assessment prior to therapy initiation.

Subjects who progress or die following an extended period of follow up will also be censored at a latest adequate assessment prior to the end of a predefined lapse window, even if information is available regarding progression or death after this extended period. Should a subject die after the end of this lapse window they will be censored at their first dose date. The lapse window after which PFS events will not be considered is defined in Section 5.7.

Otherwise, if a subject does not have documented progression, the subject will be censored at the latest adequate assessment.

PFS will be listed.

Sponsor: Aduro Biotech, Inc.
Protocol Number: ADU-CL-14
Version and Date: Version 1.0, 13Mar2018

Overall Survival

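### SAP 5.6 can impute a new-therapy date that contradicts the recorded month or precedes the first dose, which distorts individual PFS, DOR and best-response records

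*SAP*

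**What the plan says.** SAP 5.6 (the part on subsequent anticancer therapy, radiotherapy and surgery) is limited to "imputation of new anti-cancer therapies taken after first study treatment". It notes that such dates are not usually imputed but may have to be when an efficacy derivation needs them. There are two branches:

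- **Day and month missing.** If PD occurred in the recorded year, therapy starts the day after PD. If not, "Otherwise the new anti-cancer therapy date will be assigned to January 1st".
- **Only the day missing.** The same year-level test is applied: "If PD has been identified in the year noted, new anti-cancer therapy date will be assigned to begin one day after" the PD date. The recorded month is used only when there was no PD that year: "Otherwise the new anti-cancer therapy date will be assigned to the 1st of the stated month".

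The adverse-event rule in the same section does guard against impossible dates. When the partial date shares its year (or month and year) with first treatment, and nothing shows the event ended earlier, it says "Otherwise, set the start date to the date of first study treatment". The new-therapy rule has no such step.

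The new-therapy date then acts as a cut-off. For best overall response (BOR), SAP 7.1 says "assessments collected after the start of new cancer treatment will not be considered". For PFS, SAP 7.2 says "Tumor assessments taken after switch to another anti-cancer therapy will be excluded from consideration". If therapy starts before PD, SAP 7.2 censors PFS at the last adequate scan before therapy. If no adequate scan remains, it censors at the first dose, unless the subject died before a first assessment. DOR follows similar censoring.

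**The concern.** An imputed date should agree with the part of the date that was recorded and with the scope of the rule that creates it. The two branches fail in different ways.

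(a) A known month is discarded whenever PD falls anywhere in the same year. If the true order was new therapy and then PD, the rule reverses it. A record that should be censored is listed as a PFS event, and a response seen only after the switch can be credited to the study regimen.

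(b) A year-only date without PD that year goes to 1 January with no lower bound. In the year of first dose, that puts therapy before study treatment, although the rule covers only therapies begun after it. No post-baseline scan then survives the cut-off, so a responder can be derived as not evaluable and lose the DOR record.

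The errors run in opposite directions: (a) can lengthen PFS time and improve BOR, while (b) erases both. A one-sided caveat would not cover them.

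**Working it through.** The plan states no figure on this point, so there is none to reproduce. I applied the SAP rules to illustrative subjects.

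**Inputs from the documents**
- Date rules: SAP 5.6. Cut-offs and censoring: SAP 7.1 and 7.2.
- Time in days = event or censoring date − first dose date + 1; weeks = days / 7 (SAP 5.3).
- Scans about every 6 weeks, taken as 42 days (SAP 3.1).

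**Assumptions (not trial data)**
- First dose 6 Mar 2017. Scans on 17 Apr (day 43), 29 May (day 85), 10 Jul (day 127), 21 Aug (day 169) and 2 Oct 2017 (day 211).
- Subjects are alive, and only scans dated before new therapy count.

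| Case | Recorded therapy date | Scans | SAP imputes | Result under SAP | Result with a date consistent with the record |
|---|---|---|---|---|---|
| A | Jun 2017 | SD, SD, PR, PR, PD | 3 Oct 2017 | BOR PR; event day 211 (30.14 wk) | BOR SD; censored day 85 (12.14 wk) |
| A′ | May 2017 | as A | 3 Oct 2017 | BOR PR; event day 211 (30.14 wk) | BOR SD; censored day 43 (6.14 wk) |
| A2 | Sep 2017 | SD, PD (29 May) | 30 May 2017 | BOR SD; event day 85 | the same |
| B | 2017 | SD, PR, PR, PR; no PD | 1 Jan 2017 | BOR not evaluable; censored day 1 (0.14 wk) | BOR PR; censored day 169 (24.14 wk) |

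**Branch (a).** In case A, PD on 2 Oct 2017 passes the year test, so therapy is set to 2 Oct + 1 = 3 Oct and June is ignored. The July and August responses and the October PD, all after the switch, are kept. Using 1 June or 28 June gives the same corrected result; in A′, so do 1 May and 28 May. Case A2 shows the limit: when the recorded month follows PD, the month is still overridden but neither BOR nor PFS changes.

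**Branch (b).** In case B the imputed date is 64 days before first dose (30 days left in January + 28 in February + 6 in March). All four scans fall after it and are dropped. The corrected column assumes therapy truly began on 15 Nov 2017. DOR would then be censored at 21 Aug − 29 May + 1 = 85 days; under the SAP rule the subject has no DOR record. Moving the date up to first dose does not help, because every post-baseline scan is still later than the cut-off: BOR stays not evaluable and PFS stays at day 1.

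**First-of-month default.** This can also precede dosing. Therapy recorded as March 2017 without PD becomes 1 Mar, before the assumed first dose on 6 Mar.

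**How often 1 January precedes dosing.** It does so for any first dose in the recorded year, apart from one on 1 January itself. The original protocol is dated 20 Dec 2016, 12 days before 1 Jan 2017. If first doses fell in 2017, every year-only 2017 record without PD that year is affected. No first-dose date is given, so this is an inference.

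**The case against.** The strongest reply is that little depends on the rule. SAP 2, 7 and 11 say efficacy is listed and not summarised, SAP 7.1 and 7.2 keep ORR and DCR out of the report synopsis, and SAP 13.3 plans no figures. A reader might infer a biased response rate or Kaplan-Meier curve; the documents do not support that, because neither will be produced. This stands and limits the size of the point. It does not remove it, since the PFS and DOR listings are still derived outputs.

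Second, the raw data stay visible. SAP 13.2 lists subsequent therapy, response assessments and lesion data, and protocol 8.4 sends missing data back to the sites. No partial date is shown to exist. That also stands, although a reader would have to notice the conflict unaided.

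Third, branch (a) does harm only if a scan is taken after the switch. Subjects off all study drugs without PD are imaged only until PD or new therapy (SAP 3.1), and protocol 6.3.8 bars non-study chemotherapy and immunotherapy during the study. This makes (a) uncommon but not impossible: 5.6 also covers radiotherapy, and 6.3.8 lets a subject given a prohibited therapy continue dosing with Medical Monitor approval, hence with scheduled scans. Branch (b) is untouched, because it deletes valid scans taken on study treatment.

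A reader might also infer date errors of up to eleven months, with many months of scans on another drug credited to the study. That needs a January switch and a December PD in one year. For 2017 it would mean dosing and switching within 42 days of the original protocol date (20 Dec 2016 to 31 Jan 2017). For 2018, all end-of-treatment visits were done by 31 Jan and no further follow-up was expected (SAP 3.5). The trial's timeline does not support it.

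**Conclusion.** The rule is wrong as written in both branches. Branch (a) overrides recorded data, with consequences only when the stated month precedes PD and a scan follows the switch. Branch (b) gives a date outside the rule's own scope whenever a year-only record without PD that year falls in the year of first dose; any subject with evaluable post-baseline scans then loses all of them.

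The effect per affected record can be complete. In the illustrations, a censoring at day 85 becomes an event at day 211, and a partial response censored at day 169 becomes not evaluable at day 1. It reaches derived BOR and the PFS and DOR listings and no reported summary estimate. The number of affected subjects cannot be derived because the documents give no count of partial dates. This is a drafting correction to make before the listings are final; it does not threaten a trial conclusion.

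**What to change.** Amend the new-therapy bullets in SAP 5.6:

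- **Only the day missing.** Use PD + 1 only if PD falls in the stated month and year. Otherwise use the 1st of the stated month, moved to the day after the last study dose (or, failing that, the first dose) only if that dose falls in the same month. Always keep the date inside the stated month.
- **Day and month missing.** Use PD + 1 if PD falls in that year. Otherwise use the later of 1 January and the day after the last study dose, capped at 31 December of the stated year.
- **Both branches.** Never impute a date before first dose, and flag imputed dates in the listings.

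Do not add a blanket rule that therapy can never start on or before the last study dose. It could override a known month or year, repeating the fault in (a). It would also clash with PD + 1, because the protocol (6.1 and 11) allows dosing to continue beyond RECIST progression.

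The year-only default remains approximate: scans taken after the last dose but before the true start of new therapy would be lost. The flag lets a reader see that. The cost is a few lines of SAP text, the derivation program and one indicator in the affected listings. No new data are needed.
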